| | 0.90 | 0.3843 |
| 0.50 | 0.25 | 0.9958 |
| | 0.45 | 0.8852 |
| | 0.60 | 0.7764 |
| | 0.75 | 0.7431 |
| | 0.90 | 0.7385 |

F. Arm 3 Frontline Elderly AML cohort (AZA + VEN + Nivo) (N=30)

Historical data for frontline patients treated with venetoclax and hypomethylating agents (DiNardo CD et al, Blood. 2019 Jan 3;133(1):7-17); Pollyea D et al ASH 2018 Oral presentation Abstract 285.: full PowerPoint attached as Appendix) show ORR of 66%. It is expected for the current trial that the

Nivolumab and azacytidine

three-drug combination will improve the ORR by 15-20% while the toxicity rate is maintained at or below 30%. A sample size of 30 patients ensures that, if the trial is not terminated early, a posterior 90% credible interval for ORR will have width of 0.28 at most, under the assumption of a 80% of ORR. The prior probabilities of ORR and toxicity for the experimental regimen are modeled by beta distributions (*Beta* (1.2, 0.8) and *Beta* (0.6, 1.4), respectively. Denoting the historical proportion of overall response rate and toxicity rate by $\{p(\text{ORR}, H) = 0.60, p(\text{TOX}, H) = 0.30\}$, the following decision criteria will be applied:

- 1) Stop if $\text{Prob}\{p(\text{ORR}, H) + \delta_{\text{OR}} > p(\text{ORR}, E) \mid \text{data}\} > 0.95$, where $\delta_{\text{OR}} = 0.2$
- 2) Stop if $\text{Prob}\{p(\text{TOX}, H) + \delta_{\text{TOX}} < p(\text{TOX}, E) \mid \text{data}\} > 0.90$, where $\delta_{\text{TOX}} = 0$

Patients will be monitored in cohorts of 5 according to the following stopping boundaries for overall response and toxicity.

| # Patients Evaluated | Stop this cohort if \leq this # ORR | Stop if \geq this # toxicities |
|----------------------|---------------------------------------|-------------------------------------|
| 5 | 0-2 | 4-5 |
| 10 | 0-5 | 6-10 |
| 15 | 0-9 | 8-15 |
| 20 | 0-12 | 10-20 |
| 25 | 0-16 | 12-25 |
| 30 | Always stop with this many patients | Always stop with this many patients |

The operating characteristics are summarized in the following table (based on simulations from 10,000 trials).

| True Toxicity Rate | True ORR Rate | PROB(Stop Early) |
|--------------------|---------------|------------------|
| 0.10 | 0.60 | 0.7956 |
| | 0.70 | 0.4433 |
| | 0.80 | 0.1221 |
| | 0.85 | 0.0441 |
| | 0.90 | 0.0114 |
| 0.20 | 0.60 | 0.7985 |
| | 0.70 | 0.4511 |
| | 0.80 | 0.1344 |
| | 0.85 | 0.0575 |
| | 0.90 | 0.0252 |
| 0.30 | 0.60 | 0.8180 |
| | 0.70 | 0.5041 |
| | 0.80 | 0.2180 |
| | 0.85 | 0.1485 |
| | 0.90 | 0.1194 |
| 0.40 | 0.60 | 0.8740 |
| | 0.70 | 0.6569 |
| | 0.80 | 0.4589 |
| | 0.85 | 0.4109 |
| | 0.90 | 0.3907 |
| 0.50 | 0.60 | 0.9465 |
| | 0.70 | 0.8543 |
| | 0.80 | 0.7702 |

| Nivolumab and azacytidine | | |
|---------------------------|---------------|------------------|
| True Toxicity Rate | True ORR Rate | PROB(Stop Early) |
| | 0.85 | 0.7498 |
| | 0.90 | 0.7412 |

The Investigator is responsible for completing an efficacy/safety summary report, and submitting it to the IND Office Medical Affairs and Safety Group, for review and approval. This should be submitted as follows:

Lead-in Phase:

Every 6 evaluable patients complete cycle 1 of study therapy before advancing/changing dose levels.

Expansion Phase:

After the first 5 evaluable patients per cohort, complete 3 months of study treatment, and every 5 evaluable patients per cohort, thereafter.

A copy of the cohort summary should be placed in the Investigator's Regulatory Binder under "sponsor correspondence".

Statistical Analysis Plan

All patients who received any dose of the study agent will be included in the analysis for efficacy and safety. Demographic/clinical characteristics (including duration of response) and safety data of the patients will be summarized using descriptive statistics such as mean, standard deviation, median and range. For the primary efficacy analysis, we will estimate the ORR for the combination treatment, along with the 95% confidence interval. Patients who drop out of the study before completing all the cycles will be treated as "failures" for the primary analysis. Overall response rate (ORR) during the study period will also be presented with the 95% confidence interval. The association between ORR and patient's clinical characteristics will be examined by Wilcoxon's rank sum test or Fisher's exact test, as appropriate. Toxicity type, severity and attribution will be summarized for each patient using frequency tables.

The distribution of time-to-event endpoints (DFS and OS) including overall survival and progression free survival will be estimated using the method of Kaplan and Meier.

Comparisons of time-to-event endpoints by important subgroups will be made using the log-rank tests. Paired t-tests will be used to determine the immunological and molecular changes in the peripheral blood and bone marrow from baseline to the time of response, and to the time of disease progression. Correlation analysis (such as logistic regression analysis) will be conducted to determine the relationship between induction of hypomethylation / DNA damage and clinical response.

Statistical analysis of biomarker data: Descriptive statistics including plots, mean, median and standard deviations will be used to summarize data. For continuous outcomes, t-test and ANOVA will be used to compare outcome measures across patient characteristics.

Dunnett's and Tukey's test that properly adjust for multiplicity in multiple tests will be implemented. Pair-wise comparisons will be performed using pre- and post-therapy samples from each patient. The chi-square test or Fisher's exact test will be used to test the association between two categorical variables such as disease state and performance status.

Both univariate and multivariate logistic regressions will be performed to model prognostic factors.

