|--------------------|----------|----------------------------|
| 0.10 | 0.15 | 0.8503 |
| | 0.20 | 0.5344 |
| | 0.25 | 0.2466 |
| | 0.30 | 0.0967 |
| | 0.35 | 0.0377 |

| Nivolumab and azacytidine | | |
|---------------------------|-------------|---------------|
| | 0.40 | 0.0157 |
| 0.20 | 0.15 | 0.8527 |
| | 0.20 | 0.5419 |
| | 0.25 | 0.2587 |
| | 0.30 | 0.1112 |
| | 0.35 | 0.0532 |
| | 0.40 | 0.0315 |
| 0.30 | 0.15 | 0.8752 |
| | 0.20 | 0.6118 |
| | 0.25 | 0.3718 |
| | 0.30 | 0.2469 |
| | 0.35 | 0.1977 |
| | 0.40 | 0.1793 |
| 0.40 | 0.15 | 0.9500 |
| | 0.20 | 0.8446 |
| | 0.25 | 0.7485 |
| | 0.30 | 0.6985 |
| | 0.35 | 0.6788 |
| | 0.40 | 0.6714 |
| 0.50 | 0.15 | 0.9959 |
| | 0.20 | 0.9872 |

Table 11. Operating characteristics for simultaneous monitoring response and toxicity rates for patients treated with combination treatment

| True Toxicity Rate | True ORR | Prob(stop the trial early) |
|--------------------|----------|----------------------------|
| | 0.25 | 0.9792 |
| | 0.30 | 0.9751 |
| | 0.35 | 0.9735 |
| | 0.40 | 0.9729 |

B. Arm 1 Newly diagnosed older AML (≥ 65 years) cohort (Aza+Nivo) (N=40: closed to accrual as of 11/1/2019, Total Accrual to date was 15 patients)

Historical data on similar patients show an ORR of 18-25% [the historical response rate in older newly diagnosed AML (≥ 65 years) with single agent hypomethylator therapy (5-azacytidine or decitabine) in three large randomized phase II trials was 17.5 % with decitabine alone in patients with AML (Kantarjian et al., JCO 2012), 18% with azacytidine alone in patients with AML and blasts 20-30% (Fenaux et al., JCO 2010), and 27.8% with azacytidine alone in patients with AML and blasts $>30\%$ (Dombret et al., Blood 2015)]. The target ORR with the experimental treatment is 40%. This regimen of the combination treatment will be considered worthy of further investigation if it elicits an increase in ORR to 40% with acceptable toxicity. A $>30\%$ drug-related grade 3/4 toxicity rate is considered unacceptable. Thus, interim monitoring rules, assuming the prior distributions below, were constructed that meet the following two conditions,

3) Stop if $\text{Prob}\{ p(\text{ORR}, E) < p(\text{ORR}, H) + 0.15 \mid \text{data} \} > 0.99$, or
 4) Stop if $\text{Prob}\{ p(\text{TOX}, E) > 0.30 \mid \text{data} \} > 0.95$,

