where $P(\text{ORR}, E)$ and $P(\text{TOX}, E)$ are the true ORR and toxicity rates for the combination treatment, and $p(\text{ORR}, H)$ is the true ORR rate of the standard treatment. The first rule provides for stopping the study if the data suggest that it is unlikely (i.e., probability < 1%) that ORR rate of the combination treatment is greater than the ORR rate of standard treatment by 15.0%. The second condition will stop the study early if excessive therapy-related grade 3/4 toxicity (>30%) is highly probable (i.e., probability >95.0%) for the combination treatment. Monitoring for toxicity and futility will not begin until 6 patients have been evaluated, and cohort size for future evaluations is 4.

The monitoring rule for the toxicity rate, based on these assumptions and monitoring conditions above is found in Table 12. **For example, accrual will cease if 5 or more patients experience toxicities among the first 8 patients.**

| Table 12. Stop accrual if the number of drug-related grade 3/4 toxicities is greater than or equal to indicated (i.e., # patients with toxicities) among the number of patients evaluated | | | | | | | | | | |
|---|---|-----|------|------|-------|-------|-------|-------|-------|-------------------------------------|
| # patients evaluated | 4 | 8 | 12 | 16 | 20 | 24 | 28 | 32 | 36 | 40 |
| # patients with toxicities | 4 | 5-8 | 7-12 | 9-16 | 10-20 | 12-24 | 13-28 | 15-32 | 16-36 | Always stop with this many patients |

Monitoring the ORR rate, based on the above assumptions and monitoring conditions is found in Table 13. **For example, accrual will cease if no patient experience an overall response within 3 months of initiation of therapy in the first 8 patients treated.**

| Table 13. Stop accrual if the number with overall response is less than or equal to indicated (i.e., # patients with overall response) among the number of patients evaluated | | | | | | | | | | |
|---|------------------------------------|---|-----|-----|-----|-----|-----|-----|-----|-------------------------------------|
| # patients evaluated | 4 | 8 | 12 | 16 | 20 | 24 | 28 | 32 | 36 | 40 |
| # patients with overall response | Never stop with this many patients | 0 | 0-1 | 0-2 | 0-3 | 0-4 | 0-5 | 0-6 | 0-8 | Always stop with this many patients |

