Multi Lean Desktop (version 2.1.0) was used to generate the toxicity and futility stopping boundaries and the OC table (Table 14). In order to utilize the software for the design, a 25% constant rate, and beta(0.5,1.5) priors were assumed for the standard treatment response distribution and experimental treatment response prior distribution, respectively. In addition, a 30% toxicity constant rate and beta (0.6, 1.4) priors were assumed for the standard treatment toxicity constant rate and experimental treatment toxicity prior distribution, respectively.

The probability of stopping the study early if the true ORR of the combination treatment was 30% and the true toxicity rate was 30% was 17.6%. Probabilities of stopping early for high true toxicity rates (i.e., 50%) were 86.5% when the true ORR was 40% and 93.1% when true ORR rate was 25%.

Table 14. Operating characteristics for simultaneous monitoring response and toxicity rates for patients treated with combination treatment

| True Toxicity Rate | True ORR | Prob(stop the trial early) |
|--------------------|-------------|----------------------------|
| 0.10 | 0.25 | 0.5185 |
| | 0.35 | 0.1345 |
| | 0.40 | 0.0558 |
| | 0.45 | 0.0217 |
| | 0.50 | 0.0083 |
| 0.20 | 0.25 | 0.5254 |
| | 0.35 | 0.2975 |
| | 0.40 | 0.0694 |
| | 0.45 | 0.0358 |
| | 0.50 | 0.0226 |
| 0.30 | 0.25 | 0.5797 |
| | 0.35 | 0.2446 |
| | 0.40 | 0.1759 |
| | 0.45 | 0.1461 |
| | 0.50 | 0.1344 |
| 0.40 | 0.25 | 0.7494 |
| | 0.35 | 0.5496 |
| | 0.40 | 0.5087 |
| | 0.45 | 0.4909 |

Table 14. Operating characteristics for simultaneous monitoring response and toxicity rates for patients treated with combination treatment

| True Toxicity Rate | True ORR | Prob(stop the trial early) |
|--------------------|----------|----------------------------|
| 0.50 | 0.50 | 0.4840 |
| | 0.25 | 0.9309 |
| | 0.35 | 0.8759 |
| | 0.40 | 0.8646 |
| | 0.45 | 0.8597 |
| | 0.50 | 0.8578 |

C. Arm 2 First and Second Salvage AML cohort (AZA + Nivo + Ipi)

Historical data on similar patients show an ORR of 12-15%. The target ORR with the experimental treatment is 30%. This regimen of the combination treatment will be considered worthy of further investigation if it elicits an increase in ORR to 30% with acceptable toxicity. A >30% drug-related grade 3/4 toxicity rate is considered unacceptable. Thus, interim monitoring rules, assuming the prior distributions below, were constructed that meet the following two conditions,

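### Arm 1 frontline cohort: the 17.6% early-stopping probability is labelled with a 30% ORR but belongs to 40%, and one Table 14 cell (0.2975) should be 0.1470

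*Combined protocol and SAP*

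**What the plan says.** Section 11.3 B of the combined protocol and SAP sets two stopping rules for newly diagnosed older patients in Arm 1:

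- Futility: "3) Stop if $\text{Prob}\{ p(\text{ORR}, E) < p(\text{ORR}, H) + 0.15 \mid \text{data} \} > 0.99$, or"
- Toxicity: "4) Stop if $\text{Prob}\{ p(\text{TOX}, E) > 0.30 \mid \text{data} \} > 0.95"

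The inputs are a "25% constant rate, and beta(0.5,1.5) priors were assumed for the standard treatment response distribution" and the experimental response prior respectively, and for toxicity "a 30% toxicity constant rate and beta (0.6, 1.4) priors were assumed". The target ORR is 40%. Tables 12 and 13 turn the rules into boundaries at 4, 8, ..., 36 patients, and Table 14 lists the probability of stopping early.

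The paragraph before Table 14 says that the probability of stopping early when the true ORR "was 30% and the true toxicity rate was 30% was 17.6" percent. It then gives 86.5% (ORR 40%, toxicity 50%) and 93.1% (ORR 25%, toxicity 50%).

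Table 14 has lines for ORR 0.25, 0.35, 0.40, 0.45 and 0.50 in each of five toxicity blocks, 25 cells in all. It has no ORR 0.30 line. At ORR 0.35 it prints 0.1345, 0.2975 and 0.2446 for toxicity 0.10, 0.20 and 0.30.

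The heading describes the "cohort (Aza+Nivo) (N=40: closed to accrual as of 11/1/2019", with 15 patients accrued.

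**The concern.** Both figures conflict with Table 14 before anything is calculated.

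- With a futility rule, a lower true ORR makes early stopping more likely. At toxicity 0.30, Table 14 gives 0.2446 at ORR 0.35, so the value at ORR 0.30 must be higher than that. The text's 17.6% is lower.
- With a toxicity rule, a higher true toxicity rate makes early stopping more likely. At ORR 0.35 the printed values rise from 0.1345 to 0.2975 and then fall to 0.2446. That order is impossible.

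These are the stated properties of the design behind Part b primary objective 2, ORR in older newly diagnosed patients given nivolumab with 5-azacytidine. A reader who wants the chance of stopping at an ORR of 30% would take 17.6% from the text and could not check it against Table 14, which has no such line.

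**Working it through.** **Inputs** (all from section 11.3 B)

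- Maximum N = 40; looks at 4, 8, ..., 36. Reaching 40 is not counted as early stopping.
- Toxicity boundaries, Table 12: "4 | 5-8 | 7-12 | 9-16 | 10-20 | 12-24 | 13-28 | 15-32 | 16-36", that is, stop at or above 4, 5, 7, 9, 10, 12, 13, 15, 16.
- Response boundaries, Table 13: no stop at 4, then stop at or below 0, 1, 2, 3, 4, 5, 6, 8 at 8, 12, ..., 36.

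**Step 1: boundaries.** With k events in n patients, the rules are

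- stop for futility if P(Beta(0.5 + k, 1.5 + n − k) < 0.25 + 0.15) > 0.99;
- stop for toxicity if P(Beta(0.6 + k, 1.4 + n − k) > 0.30) > 0.95.

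These reproduce every boundary in Tables 12 and 13.

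**Step 2: stopping probability.** Taking response and toxicity as independent,

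P(stop early) = 1 − P(no futility stop) × P(no toxicity stop).

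Each factor is exact. The count distribution is carried forward four patients at a time with binomial probabilities, and the mass at or beyond a boundary is removed at each look.

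| True rate | P(no stop on that endpoint) |
|---|---|
| Toxicity 0.10 | 0.99948 |
| Toxicity 0.20 | 0.98510 |
| Toxicity 0.30 | 0.87238 |
| ORR 0.30 | 0.71308 |
| ORR 0.35 | 0.86592 |
| ORR 0.40 | 0.94465 |

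**Step 3: reproduce the plan's figures, then the disputed ones.**

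| Toxicity, ORR | Calculation | Result | Printed |
|---|---|---|---|
| 0.10, 0.35 | 1 − 0.99948 × 0.86592 | 0.1345 | 0.1345 |
| 0.30, 0.35 | 1 − 0.87238 × 0.86592 | 0.2446 | 0.2446 |
| 0.30, 0.40 | 1 − 0.87238 × 0.94465 | 0.1759 | 0.1759 |
| **0.20, 0.35** | 1 − 0.98510 × 0.86592 | **0.1470** | **0.2975** |
| 0.20, 0.30 | 1 − 0.98510 × 0.71308 | 0.2975 | no line |
| **0.30, 0.30** | 1 − 0.87238 × 0.71308 | **0.3779** | **17.6% (text)** |

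Over the whole of Table 14, 24 of 25 cells match to four decimals. The exception is toxicity 0.20, ORR 0.35. The text's 86.5% and 93.1% also reproduce (0.8646 and 0.9309).

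**Step 4: check from the printed table alone.** Under independence, the ratio of (1 − entry) at ORR 0.35 to (1 − entry) at ORR 0.40 is the same in every toxicity block. The printed table gives 0.9166, 0.7549, 0.9166, 0.9168 and 0.9165 for toxicity 0.10 to 0.50, so only the 0.20 block is out of line. The neighbouring cells imply

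1 − (1 − 0.1345) × (1 − 0.0694) / (1 − 0.0558) = 0.1470.

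If 0.2975 is moved to ORR 0.30, the printed cells also give the value missing from the text:

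1 − (1 − 0.2975) × (1 − 0.1759) / (1 − 0.0694) = 0.3779.

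**Step 5: look schedule.** The text says "Monitoring for toxicity and futility will not begin until 6 patients have been evaluated, and cohort size for future evaluations is 4", while the tables start at 4. Neither variant rescues the two figures:

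| Looks | Toxicity 0.20, ORR 0.35 | Toxicity 0.30, ORR 0.30 |
|---|---|---|
| 4, 8, ..., 36 (tables) | 0.1470 | 0.3779 |
| 8, 12, ..., 36 | 0.1464 | 0.3769 |
| 6, 10, ..., 38 | 0.1612 | 0.3858 |

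**The case against.** **The number in the text is probably right and its label wrong.** 17.6% is correct for the 40% target. The matching sentences for the two earlier salvage cohorts (sections 11.3 A and C) quote the probability at their own target, 30% (24.7% against 0.2469 in Table 11; 16.9% against 0.1694 in Table 17). The next sentence in 11.3 B uses 40% and 25%. A 30% carried over from a salvage cohort is the likeliest explanation. This stands. A reader might infer that the design understates its chance of early stopping by 20 points, but that gap exists only if the 30% label is kept.

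**The table error is one cell away from the design points.** ORR 0.35 is neither the historical nor the target rate, and toxicity 0.20 is below the 30% limit. This also stands. A reader might infer that the error rates for this objective are wrong in general. They are not: every cell at ORR 0.25 and 0.40 is right.

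**Nothing in the conduct depends on it.** The boundaries are correct, the cohort is closed, and the planned primary analysis is an ORR with a 95% confidence interval, which uses no operating characteristic. This stands and sets the weight of the point.

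**It could be a fault of PDF extraction.** This is unlikely. The ORR 0.30 line is absent from all five toxicity blocks, whereas the corresponding Arm 2 frontline table has it. The stray cell equals the adjacent ORR's value to four decimals, and the text error is in running prose.

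**It overlaps with Arm 2.** Section 11.3 D repeats the same sentence for a 30-patient cohort whose own table gives 0.3326, 0.7636 and 0.8554 for the three scenarios. That is a separate error. Correcting 11.3 D would leave 11.3 B wrong.

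**Conclusion.** The point holds as a minor correction to the stated design properties.

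- **Text:** 17.6% is set against a true ORR of 30% but belongs to 40%. If 30% is kept, the figure should be 37.8%, a difference of 37.8 − 17.6 = 20.2 percentage points. If the label becomes 40%, 17.6% stands.
- **Table 14:** toxicity 0.20, ORR 0.35 should read 0.1470. The printed 0.2975 is too high by 0.2975 − 0.1470 = 0.1505, about 15 points.

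The documents do not support reading this as a faulty stopping rule or as something that affected the cohort. The boundaries follow from the stated priors and cutoffs, and accrual ended at 15 patients.

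The result assumes the look schedule of Tables 12 and 13 and independence of response and toxicity. Agreement with the other 24 cells to four decimals indicates that the plan's own calculation used both. That the slips arose from a deleted ORR 0.30 line and a carried-over label is an inference; the corrected values do not depend on it.

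**What to change.** 1. In the paragraph before Table 14, change the true ORR attached to 17.6% from 30% to 40%. Alternatively, keep 30% and print 37.8%.
2. In Table 14, at toxicity 0.20 and ORR 0.35, replace 0.2975 with 0.1470.
3. Only if the text keeps 30%, add an ORR 0.30 line so that the figure can be looked up: 0.2873, 0.2975, 0.3779, 0.6291 and 0.8978 for toxicity 0.10 to 0.50. With 40% in the text this line is optional.

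The cost is one label and one cell, which one run of the design software named in the plan can confirm. No boundary, sample size or analysis changes.
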